5.4 Agent Administration

5.4.1 Neratinib

Neratinib is administered orally once daily, continuously with no breaks, on days 1-28 of a 4-week (28-day) cycle, +/- 3 days. Neratinib is dosed as 240 mg once daily (six 40 mg tablets). Dosing is not weight-based. Patients should take neratinib at approximately the same time of day every day, preferably in the morning, with food. The dose is considered “missed” if not taken within approximately 12 hours of the usual administration time. Doses should not be retaken if skipped, missed, or vomited. Tablets must be swallowed whole; they may not be crushed, chewed, or dissolved.

Neratinib requires the use of anti-diarrheal prophylaxis with loperamide and colestipol (see Sections 5.3.3). Investigators must ensure that participants have loperamide and colestipol on hand when starting to take the investigational product. Loperamide and colestipol are the standard anti-diarrheal therapies in this study. If alternative anti-diarrheal medication is used, the reason must be documented in the source documents. Acceptable reasons are non-tolerance of standard therapies or lack of efficacy. Loperamide and colestipol will be dispensed directly by the site on day 1 of each cycle.

Dose modifications are delineated in section 6. If significant treatment-related toxicities have not recovered to Grade ≤ 1 or baseline grade, the patient may skip up to 28 days from the last scheduled dose. Patients should be re-evaluated weekly during the delay whenever possible. Patients randomized to the fulvestrant arm (Arm A) may continue

fulvestrant dosing while neratinib is held, as long as the toxicity is felt to be unrelated to fulvestrant.

Dosing may also be suspended for up to 28 days for unanticipated intercurrent medical events that are not associated with study treatment toxicity or disease progression.

Patients are to fill out a pill diary for every cycle (Appendix B) and return it to clinic staff at the end of each cycle.

5.4.2 Fulvestrant

Fulvestrant is administered intramuscularly on Cycle 1 Day 1, Cycle 1 Day 15, and then on Day 1 of each subsequent 4-week (28-day) cycle +/- 3 days. Fulvestrant is dosed as 250 mg/5mL (x2) for a total of 500 mg via intramuscular injection. Administer intramuscularly slowly in the buttock. (NOTE: 500 mg dose will require one 250 mg injection in each buttock). Immediately activate needle protection device upon withdrawal from patient by pushing lever arm completely forward until needle tip is fully covered. Visually confirm that the lever arm has fully advanced and the needle tip is covered. If unable to activate, discard immediately into an approved sharps container.

No dose modifications are allowed. If a patient has an intolerable toxicity felt to be related to fulvestrant, fulvestrant dosing can be held for up to 28 days (1 cycle) to allow the toxicity to recover to baseline or grade ≤ 1 . Neratinib dosing can continue while fulvestrant is held. Commercial supply of fulvestrant will be used.

5.4.3 Mandatory Diarrhea Prophylaxis

Diarrhea is the major dose-limiting toxicity of neratinib, with onset typically occurring early in the course of treatment (during the first few days of the first cycle of treatment). Primary prophylactic use of antidiarrheal medication is mandatory for all patients taking neratinib. Loperamide and colestipol are the required standard therapies to treat diarrhea. Second-line antidiarrheal treatments and adjunctive therapies (i.e., octreotide [SANDOSTATIN®]) (or equivalent)) are also recommended for use when appropriate. The Investigator must review with the patient the Patient Instructions for the management of diarrhea in Appendix C.

The patient should be given clear instructions to contact the Investigator in the event of persistent Grade ≥ 2 diarrhea to discuss the appropriate course of treatment. Loperamide and colestipol should be dispensed directly with neratinib. It is very important to initiate treatment with loperamide and colestipol concomitantly with the first dose of neratinib to minimize occurrence and severity of diarrhea.

Refer to protocol Section 6.1.2, Table 2 for Dose Adjustment of Neratinib as applicable.

The Investigator or suitably trained and qualified delegate (e.g., MD, RN, NP, etc.) must

contact the patient by phone on Cycle 1 Day 2, Cycle 1 Day 3, and Cycle 1 Day 4 after the first dose of neratinib to inquire about compliance with loperamide and colestipol, diarrhea or any other adverse events. (These phone calls are very important and should be recorded in the clinical records together with response from the patient and action taken.)

Patients should be instructed to promptly report diarrhea symptoms and to report the number of stools per day and the dose of any anti-diarrheal medication taken each day for the first 28 days of therapy.

5.4.3.1 Loperamide (Imodium ®)

For the first 14 days, loperamide 4 mg (2 tablets/capsules) will be self-administered orally 3 times a day (total 12 mg a day). The initial dose of loperamide will be administered orally with the first dose of neratinib. After the first 14 days, loperamide 4 mg (2 tablets/capsules) will be administered orally twice a day (total 8 mg a day) through the first cycle of therapy (Day 28) from start of neratinib dosing, whether the patient is experiencing diarrhea or not. Thereafter, loperamide will be administered as needed (not to exceed 16 mg per day) per the investigator's discretion. Commercial supply of loperamide will be used and provided by research pharmacies (cost covered by ██████████)

Loperamide Dosing

Day	Loperamide Dose
1-14	Daily dose of 12 mg in 3 divided doses of 4 mg
15-28	Daily dose of 8 mg in 2 divided doses of 4 mg
>28	Daily dose as needed (not to exceed 16 mg per day)

Loperamide Dose Adjustment

Patients are expected to take loperamide prophylaxis as directed. However, patients may require individualization of loperamide prophylaxis dose (up to a maximum dose of 16 mg per day) with the goal of titrating to 1-2 bowel movements a day.

- For patients who develop diarrhea during Cycle 1, loperamide should be increased up to a maximum of 16 mg a day.
- If a patient is unable to tolerate loperamide due to symptomatic constipation, loperamide should be held until after the first bowel movement and then resumed at a dose reduced by one level from their current level.
- For recurrent symptomatic constipation events, hold loperamide until after the first bowel movement and then resume at a dose reduced to the next lower dose level.
- If a patient is unable to tolerate once-daily loperamide due to constipation, hold loperamide and discuss subsequent loperamide dosing with the Investigator or suitably trained and qualified delegate.
- Neratinib dosing should continue if loperamide is held.

Recommended dose reductions for loperamide are listed in the table below.

Loperamide Dose Reduction Levels for Constipation.

Dose Level	Loperamide Dose	Tablets/Capsules per day
0	4 mg TID	6 tablets/capsules a day
-1	4 mg BID	4 tablets/capsules a day
-2	2 mg TID	3 tablets/capsules a day
-3	2 mg BID	2 tablets/capsules a day
-4	2 mg once a day	1 tablet/capsule a day

Abbreviations: BID = twice daily; mg=milligrams; TID= three times daily.

5.4.3.2 Colestipol (colestid)

Loperamide in combination with twice daily colestipol is required for 28 days at the initiation of neratinib. It is very important to initiate antidiarrheal medications (loperamide and colestipol) with the first dose of neratinib and should continue throughout the first cycle unless patients have trouble tolerating these medications. In that case, providers have the discretion to make changes in these medications. . Beyond Cycle 1, ongoing prophylaxis is discretionary per the treating provider.

Patients will self-administer oral colestipol at a dose of 2g twice daily, for the first treatment cycle (28 days).

**** NOTE: During Cycle 1: Patients should take colestipol 2 gm twice daily for 28 days, with the first dose taken at least 4 hours before neratinib and loperamide prophylaxis, and the second dose to be taken at least 2 hours after neratinib and loperamide prophylaxis****

Commercial supply of colestipol will be used and provided by research pharmacies (cost covered by ██████████)

Prior to protocol version 2, diarrhea prophylaxis consisted of loperamide in combination with daily budesonide for the first 28 days. Active patients who are taking diarrhea prophylaxis at the time of protocol version 2 activation can either complete budesonide treatment or start colestipol per the treating investigator's discretion.

5.4.3.3 Additional Anti-Diarrheal Instructions

Treatment of diarrhea (Days 1-28)

- Follow dietetic measures:
 - Stop all lactose-containing products.
 - Drink 8 to 10 large glasses of clear liquids per day.
 - Eat frequent small meals.
 - Recommend low fat regimen enriched with bananas, rice, applesauce and toast until resolution of diarrhea.
- For patients with persistent Grade 1 diarrhea (<4 stools per day above baseline) despite maximal loperamide use, Lomotil® (diphenoxylate hydrochloride and atropine sulfate) 1 tablet (2.5 mg) every 6 to 8 hours may be added (or equivalent).
- For Grade 2 diarrhea during the first 28 days (4 to 6 stools per day above baseline, despite intensive anti-diarrheal therapy), consider adding octreotide (short-acting) 150

- µg subcutaneous [SC] injection 3 times a day, or after initial dose of short-acting octreotide, if well tolerated, a single dose of octreotide LAR 20 mg by intramuscular (IM) injection (or equivalent).
- After resolution of diarrhea, loperamide prophylaxis can be decreased in 2-mg decrements with the goal of titrating to 1-2 bowel movements a day.

For new onset uncomplicated Grade 1 or Grade 2 diarrhea (>28 Days and beyond)

Dietetic measures

- Stop all lactose-containing products.
- Drink 8 to 10 large glasses of clear liquids per day.
- Eat frequent small meals.
- Recommend low fat regimen enriched with bananas, rice, applesauce and toast until resolution of diarrhea.

Pharmacological Treatment

- Administer loperamide: initial dose of 4 mg (2 tablets/capsules) with the first bout of diarrhea followed by 2 mg (1 tablet/capsule) every 4 hours or after every unformed stool (maximum 16 mg a day) and continue loperamide at this frequency until diarrhea free for 12 hours.
- For patients with persistent Grade 1 diarrhea on a maximum dose of loperamide (16 mg per day) Lomotil (diphenoxylate hydrochloride and atropine sulfate) 1 tablet (2.5 mg) every 6 hours to 8 hours may be added (or equivalent).
- For Grade 2 diarrhea during the first 28 days of treatment (4 to 6 stools per day above baseline, despite intensive antidiarrheal therapy), consider adding octreotide (short acting) 150 µg SC TID; or after initial dose of short-acting octreotide, if well tolerated, a single dose of octreotide LAR 20 mg IM (or equivalent medication).

For Grade 3 or Grade 4 diarrhea with complicating features (dehydration, fever, and/or Grade 3-4 neutropenia)

Dietetic measures (same as above)

Pharmacologic treatment

- Administer loperamide: initial dose of 4 mg (2 tablets/capsules) with the first bout of diarrhea followed by 2 mg (1 tablet/capsule) every 4 hours or after every unformed stool (maximum 16 mg a day) and continue loperamide at this frequency until diarrhea free for 12 hours. Then titrate the amount of loperamide used to keep diarrhea controlled (<4 stools/day).
- Administer octreotide (100-150 µg SC BID or intravenously (IV) (25-50 µg/h) if dehydration is severe, with dose escalation up to 500 µg SC TID).
- Use IV fluids as appropriate.
- Consider prophylactic antibiotics as needed (e.g., fluoroquinolones) especially if diarrhea is persistent beyond 24 hours or there is fever or Grade 3-4 neutropenia.
- Stool cultures should be done to exclude infectious causes of Grade 3 or 4 diarrhea or diarrhea of any grade with complicating features (dehydration, fever, and/or Grade 3 or 4 neutropenia) per the Investigator's discretion. Results from occult blood, fecal

- leukocyte stain, Clostridium difficile, Campylobacter, Salmonella, and Shigella testing, when performed, should be recorded in the clinical records.
- Patients with significant diarrhea who are unresponsive to medical treatment may require treatment interruption or dose reduction.

Patient instructions for the management of diarrhea are provided in Appendix C.

5.5 General Concomitant Medication and Supportive Care Guidelines

All concomitant medications and concomitant nonpharmacological treatments/therapies will be recorded in the medical record from 30 days prior to the signing of the informed consent form (ICF) until the Safety Follow-up Visit occurring 28 days after the last dose of neratinib. This will include the start date, stop date, generic name, and indication for treatment.

At screening, patients will be asked what medications they have taken during the previous 30 days, which medications are ongoing at the time of screening, any medical conditions that require medication, and all prior cancer therapies. At each subsequent study visit, patients will be asked what concomitant medications they are currently taking.

5.5.1 Permitted Concomitant Treatment

Any palliative and/or supportive care for cancer-related symptoms, which are not otherwise specified in the list of prohibited medications below, is permitted at the Investigator's discretion.

Specifically, the following treatments are permitted during the study:

- Standard therapies for preexisting medical conditions and for medical and/or surgical complications.
- Ovarian suppression is allowed.
- Bisphosphonates and RANK (receptor activator of nuclear factor kappa-B) ligand inhibitors (e.g., denosumab), are allowed regardless of indication.

5.5.2 Prohibited Concomitant Treatment

The following treatments are prohibited throughout the duration of the active (treatment) stage/phase of the study: Any concurrent chemotherapy, hormonal therapy (except ovarian suppression which is permitted), surgery related to cancer, anticancer immunotherapy, or other anticancer treatments including other investigational agents by oral or parenteral route.

Patients who have demonstrated control of their extra-cranial disease (defined for this purpose as objective response or SD maintained for at least 2 cycles) from study therapy, but who have developed isolated brain metastases that are felt to be treatable with radiation will be allowed to receive radiation therapy and then continue their assigned study therapy until they either experience systemic progression of their disease and/or further progression in the brain. Patients should have their study therapy held until radiation is completed. Patients can restart study therapy once clinically stable as deemed

by the investigator.

Any treatment required during the first 2 months of the Program Treatment Phase that might have an interaction with loperamide (refer to loperamide package insert) or colestipol (refer to colestipol package insert) is prohibited.

5.5.3 Potential Drug-Drug Interactions

Because there is a potential for interaction of neratinib and fulvestrant with other concomitantly administered drugs through the cytochrome P450 system, the case report form must capture the concurrent use of all other drugs, over-the-counter medications, or alternative therapies. The Overall PI should be alerted if the participant is taking any agent known to affect or with the potential to affect selected CYP450 isoenzymes. Appendix D presents guidelines for identifying medications/substances that could potentially interact with the study agent(s).

The solubility of neratinib is pH dependent and treatments that alter gastrointestinal pH such as proton pump inhibitors (PPIs), H₂-receptor antagonists, and antacids may lower the solubility of neratinib. It has been observed that a single 240-mg dose of neratinib combined with lansoprazole may decrease neratinib AUC by up to 65%. The potential PK interaction of H₂-receptor antagonists with neratinib has not been evaluated. It is unknown whether separating PPI and neratinib doses reduces the interaction. If antacids are necessary, the antacid dose and the neratinib dose should be separated by 3 hours.

When taking colestipol with neratinib and loperamide during the first 28 days (Cycle 1) there should be close monitoring during the concomitant administration with ketoconazole (and itraconazole, ritonavir, saquinavir, or erythromycin), or any other CYP3A4 inhibitor for increased signs and/or symptoms of hypercorticism. Refer to the colestid package insert for contraindications, warnings, and precautions for colestipol.

Patients taking digoxin, a P-glycoprotein (P-gp) substrate with a narrow therapeutic window, should be monitored closely. The digoxin dose should be adjusted as needed, since neratinib is an inhibitor of P-gp. Co-administration of neratinib with digoxin could result in increased digoxin levels and associated digoxin toxicity.

Patients taking oral coumarin-derivative anticoagulants (ie, warfarin and phenprocoumon) should be monitored closely and their anticoagulant dose adjusted as needed.

Avoid grapefruit juice, which is a known CYP3A4 inhibitor.

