5. TREATMENT PLAN

5.1 Treatment Regimen

Neratinib and fulvestrant will be administered in 4 week cycles, with 28 consecutive days defined as a treatment cycle. Treatment will be administered on an outpatient basis. There is no specific order of administration for neratinib and fulvestrant. Reported adverse events and potential risks are described in Section 7. Appropriate dose modifications are described in Section 6. No investigational or commercial agents or therapies other than those described below may be administered with the intent to treat the participant's malignancy.

Regimen Description					
Agent	Premedications; Precautions	Dose	Route	Schedule	Cycle Length
ARM A					
Neratinib	Loperamide and Colestipol (see Section 5.3.3)	240mg (six 40mg tablets)	Orally	Neratinib: once daily, continuous Loperamide: Days 1-28, continuous Colestipol: Days 1-28, continuous	28 days (4 weeks)
Fulvestrant		500mg (two injections of 250mg each)	Intramuscularly	Cycle 1: Day 1, 15 Cycle 2 and all subsequent cycles: Day 1	
ARM B					
Neratinib	Loperamide and Colestipol (see Section 5.3.3)	240mg (six 40mg tablets)	Orally	Neratinib: once daily, continuous Loperamide: Days 1-28, continuous Colestipol: Days 1-28, continuous	28 days (4 weeks)

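### Section 5.5.3 attaches the hypercorticism check to colestipol, although the current regimen contains no corticosteroid, and as worded it misses patients completing budesonide (minor)

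*Combined protocol and SAP*

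**What the plan says.** Section 5.5.3 contains a paragraph on Cycle 1 prophylaxis that opens with its own condition: "When taking colestipol with neratinib and loperamide during the first 28 days (Cycle 1) there should be close monitoring". It names ketoconazole, itraconazole, ritonavir, saquinavir and erythromycin, and continues: "or any other CYP3A4 inhibitor for increased signs and/or symptoms of hypercorticism. Refer to the colestid package insert". Colestipol's is the only drug label it cites.

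The regimen table in Section 5.1 gives the same entry beside neratinib in both arms: "Loperamide and Colestipol (see Section 5.3.3". Arm A adds fulvestrant. Section 5.4.1 names the same two antidiarrhoeals as the study standard. Neither place lists a corticosteroid.

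In the text available, budesonide is named only in Section 5.4.3.2, which gives the history, "Prior to protocol version 2, diarrhea prophylaxis consisted of loperamide in combination with daily budesonide for the first 28 days", and then the transition rule, "Active patients who are taking diarrhea prophylaxis at the time of protocol version 2 activation can either complete budesonide treatment or start colestipol", at the treating investigator's discretion.

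**The concern.** A monitoring instruction should name the drug that creates the risk. Here the risk is steroid excess when a CYP3A4 inhibitor is given, and the drug named is colestipol. By general drug-class knowledge, which the protocol does not itself set out, hypercorticism is a corticosteroid effect, budesonide is a corticosteroid and colestipol is not.

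Two things follow if the sentence is applied as written. Sites are told to look for steroid excess in patients whose assigned treatment does not explain it. A patient still completing budesonide, in whom the check would make sense, gets no such instruction. What is at stake is the clarity of a safety rule for a small transitional group, not the efficacy comparison.

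**Working it through.** The protocol gives no figure on this point, so the check is a comparison of the text.

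**Inputs**
- Condition for the check: taking colestipol with neratinib and loperamide in Cycle 1 (5.5.3).
- Current prophylaxis: loperamide and colestipol in both arms (5.1, 5.4.1, 5.4.3.2).
- Prophylaxis before Version 2: loperamide and daily budesonide for 28 days (5.4.3.2).
- Transition rule: complete budesonide or start colestipol (5.4.3.2).

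**Applying the condition to each kind of Cycle 1 patient**

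| Patient | Corticosteroid in assigned prophylaxis | Meets the 5.5.3 condition |
|---|---|---|
| Starts under Version 2, on colestipol | No | Yes |
| On prophylaxis at activation, switches to colestipol | None after the switch | Yes |
| On prophylaxis at activation, completes budesonide | Yes | No |

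The transition rule presents the two drugs as alternatives. A patient in the last row is not taking colestipol, so the sentence does not apply to her. She is the only one of the three with a corticosteroid still in her prophylaxis.

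**Is she covered elsewhere?**
- Section 5.5.2 bars, in the first 2 months, treatment that might interact with loperamide "or colestipol (refer to colestipol package insert) is prohibited". It does not mention budesonide.
- Section 5.5.3 also has a general CYP450 rule, introduced by reference to neratinib and fulvestrant: "The Overall PI should be alerted if the participant is taking any agent known to affect". It covers her as a participant, but does not mention budesonide or hypercorticism.
- All five inhibitors named in 5.5.3 are listed in Appendix D, again without reference to budesonide.
- Under Section 5.4.3 she is called on Days 2, 3 and 4 of Cycle 1 "to inquire about compliance with loperamide and colestipol, diarrhea or any other adverse events", which is a general enquiry.

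So general safeguards reach her, but the specific instruction does not.

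**Reach.** The exposed group is patients on prophylaxis when Version 2 was activated who stayed on budesonide, each for at most the rest of one 28-day course. The documents give neither their number nor their use of CYP3A4 inhibitors, so no count can be derived.

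**Effect on the analysis.** Both arms receive the same prophylaxis, and the sentence plays no part in the PFS definition (13.1), the sample size (13.2) or the stratified logrank test (13.4).

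**The case against.** The strongest reply is that this is a drafting slip with little room for harm. For colestipol patients it adds a check and withholds nothing. For a budesonide patient to be harmed, she must be in a short window, take a CYP3A4 inhibitor, and slip past the general safeguards. These go beyond those listed above: concomitant drugs are asked about at every visit (5.5), weight and blood pressure are taken on Cycle 1 Day 15 (Table 7), patients report stools and antidiarrhoeal doses daily for 28 days (5.4.3), and serious adverse events are reportable throughout treatment (7.3.1). All of this stands, and it is why the point is minor.

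Timing is a second objection. Appendix E, Section 3.2 allows participating institutions 90 days to approve and implement a revision that is not for a life-threatening cause. A budesonide course lasts 28 days, so a new budesonide sentence could take effect after every such patient had finished. This also stands, and the fix must work in that case.

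Third, the check is not wholly pointless in colestipol patients. Sections 5.5.1 and 5.5.2 do not expressly exclude corticosteroids for other conditions, and a patient who has just switched has had recent budesonide. That is fair, but the sentence reaches such patients only by accident and still omits the one who stays on budesonide.

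Three stronger readings are tempting, and the documents support none of them.
- *A size in days.* Table 7 marks adverse event evaluation on Cycle 1 Days 1 to 4 and next on Cycle 2 Day 1, so a reader might put the gap at 28 − 4 = 24 days. That interval is the same for every Cycle 1 patient and the rewording does not change it, so it does not measure this defect. It also overlooks the Day 15 vital signs and the 28-day reporting.
- *A leftover.* A reader might infer that the sentence was written for budesonide and had its drug name replaced. This is plausible, but the pre-Version 2 text is not available.
- *A contradiction with 5.5.2.* A reader might see a CYP3A4 inhibitor as both prohibited and merely monitored. Section 5.5.2 defers to the package inserts, which are not part of the documents, so this is at most an ambiguity.

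**Conclusion.** The point holds as a minor inconsistency of wording in the safety text. The hypercorticism check is triggered by colestipol, which does not account for the risk, and is not triggered by budesonide, which would. The first half stands whether or not anyone remains on budesonide. The second matters only while someone does.

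The conclusion rests on the text as it reads and on the drug-class facts stated above. No patient count or duration of exposure is claimed. It does not follow that budesonide patients went unobserved, only that the text gives no specific instruction for them. PFS, power and error rates are unaffected.

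**What to change.** In Section 5.5.3, remove the clause on CYP3A4 inhibitors and hypercorticism from the colestipol sentence, and keep only the reference to the colestipol package insert. Then establish whether any patient is still completing budesonide:

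- If so, add a sentence such as: *A patient completing budesonide in Cycle 1 is to be watched closely for hypercorticism while she also takes a CYP3A4 inhibitor.* It can name the same five drugs as examples.
- If not, deleting the clause is enough.

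Leave the general CYP450 alert, Appendix D and the prohibition in 5.5.2 as they are.

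The cost is one reworded or shortened sentence, with no new visit, procedure or change to the analysis. If a budesonide sentence is added, it becomes redundant once the last such patient finishes, and can be removed in a later amendment.
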